# PROCEDURES

# Recruitment procedures

We will recruit subjects for this protocol from existing Emory University databases of MSM who have consented to be re-contacted for future research opportunities (see below). We will also recruit men with print, on-line, and social media advertisements (e.g. Facebook, Instagram, Craigslist, Grindr, etc.) as have been utilized for other studies conducted by the Emory investigative team. Volunteers may be engaged directly on social media or dating sites to assess interest in research participation. We will seek permission from creator/ moderator of the private website/ group, etc. before entering and interaction. Participants will also be recruited at community engagement events held by Hope Clinic recruiters (e.g. Pride celebrations, bars or businesses

catering to MSM). We will submit all print and online advertisement copies to the Emory IRB for approval prior to launching these activities. Also, all recruiters will use 1 of 2 generalized scripts to introduce the study when approaching potential participants (see below).

Scripts used for in person contact:

# Script A.

"Hello,

My name is \_\_\_\_\_\_, I am a recruiter for the Hope Clinic at Emory University. We are currently seeking volunteers to participate in one of our HIV prevention research studies. If you have a moment, would you be interested in hearing more? If not, maybe you would like to leave us your contact information to speak at another time or take one of our flyers for future reference, thank you for your time. Enjoy your day"

If contact responds affirmatively, then their contact information will be collected for a screening phone call (see phone screen script).

If contact responds negatively or does not responds, no further contact will be attempted.

Or

# Β.

"We are here from the Emory University Hope Clinic. We would like to talk to you about volunteering in HIV prevention studies. There are several studies that you may be eligible for [give brief description of current studies]. If you would like further information, either myself or a recruiter can give you a call at a time that's convenient for you. Can I take your name and number? Thanks for your time"

If contact responds affirmatively, then their contact information will be collected for a screening phone call (see phone screen script).

If contact responds negatively or does not responds, no further contact will be attempted.

 The Hope Clinic at Emory University maintains a large study database of research participants that have agreed to be re-contacted for future research studies. Due to the nature of ongoing studies at the Hope Clinic, a large proportion of these participants are MSM. Men will be contacted by phone or email and screened by phone with the eligibility criteria for this protocol. (Please see below for scripts used by recruiters when engaging by phone and/or email). Men who are eligible will be scheduled for a screening visit.

Script used by recruiters when engaging by phone (phone calls and SMS):

# Phone

Participants who are called will be greeted by the study staff. "Hello, my name is [\_\_\_\_]. I am calling from Hope Clinic..." Staff will refer to Oral Consent and Pre-Screener.

SMS

# Script A.

Hello, I am a recruiter for research studies at the Emory University Hope Clinic. We are currently looking for volunteers to participate in one or more of our HIV prevention research studies. Would you be interested in learning more?

Thank you,

\_\_Insert Name and contact details here\_\_\_\_

If contact responds affirmatively, then their contact information will be collected for a screening phone call (see phone screen script).

If contact responds negatively or does not responds, no further contact will be attempted.

# Script B.

Hello, I am a recruiter for research studies at the Emory University Hope Clinic. We are currently looking for volunteers to participate our HIV prevention research studies. All enrolled volunteers will be compensated for their time, travel, and inconvenience. Would you be interested in learning more?

Thank you,

Insert Name and contact details here

If contact responds affirmatively, then their contact information will be collected for a screening phone call (see phone screen script).

If contact responds negatively or does not responds, no further contact will be attempted.

# or Script C.

Hello, I am a recruiter for research studies at the Emory University Hope Clinic. We are currently looking for volunteers to participate in one of our HIV prevention research studies. All enrolled volunteers will be compensated for their time, travel, and inconvenience. To learn more, please visit www.hopeclinic.emory.edu/studies/enrolling-studies.html or call [contact].

Thank you,

\_Insert Name here\_\_\_\_

If contact responds affirmatively, then their contact information will be collected for a screening phone call (see phone screen script).

If contact responds negatively or does not responds, no further contact will be attempted.

Script used by recruiters when engaging by email:

Hello my name is [ ] and I am from Emory University Hope Clinic. We are currently looking to enroll participants into a new study at the Emory University Hope Clinic. This study aims to determine the efficiency of new anti-HIV agents to prevent HIV infection in men who have sex with men and transgender women who have sex with men. Study visits range from three to four visits, and you will be compensated for your time of travel and inconvenience. If you or anyone you know may be interested or have any questions about this study, please contact [name] ([contact]) or [name] ([contact]). These are the basic qualifications to participate in the study:

1) HIV-negative men ages 18-49 years.

2) Engaged in receptive anal intercourse (bottomed) in the last 6 months.

3) Not currently taking PrEP and no current plans to initiate.

4) Willing to undergo peripheral blood draws, urethral swabs, and a rectal biopsy procedure over

a 1 week to 3 month period.

2) PRISM Health (research group in the Rollins School of Public health, [name] is a member of this group) maintains large study databases of MSM who have participated in previous research studies and have consented for future contact. Men will be contacted by phone or email and screened by phone with the eligibility criteria for this protocol (refer to number 1 under recruitment for phone and email script used by recruiters). Men who are eligible will be scheduled for a screening visit.

# Study visits

There are 3 phases for each study arm (Phase I Pre- drug, Phase II Short- course, and Phase III Steady state).

# Visit 1

# Phase I, II, and III

During the screening visit, eligible MSM will provide written informed consent after all their questions are answered in a private exam room at the Hope Clinic. Subjects will also receive an approved HIPAA statement and will be informed about the way their protected health information will be used and stored. Copies of the consent/HIPAA form for this project will not be placed in individuals' medical records since this study collects sensitive information such as HIV status and sexual orientation.

After provision of informed consent, a medical history and physical examination will be conducted by the PI to evaluate for exclusion criteria. A rapid HIV test with finger stick whole blood (Determine or other CLIA waved product) will be performed by the PI or study coordinator who will be certified in HIV counseling and testing to confirm eligibility. Peripheral blood will be drawn for a complete blood count, creatinine, and coagulation tests.

# Visit 2

Version 6 04/21/17

Participants will be randomized to one of two study arms:

Arm 1. Use of Truvada®

Arm 2. Use of Genvoya®

# Phase I

10 participants (5 in each study arm) will be enrolled in study phase 1.

Study visit 2 will occur 1-6 weeks after the screening visit. During visit 2, we will draw 4 tablespoons of blood from the participants arm. A urine sample as well as penile and urethral swabs will be collected from participants. These samples will be used at CDC to develop an assay to detect Truvada® and Genvoya® in the body compartments. All specimens will be coded with a unique numeric identifier such that the CDC laboratories that receive the specimens will be unable to link them back to the study participants. Finally, rigid sigmoidoscopy (described further below) will be performed and, rectal secretions will be collected with Dacron swabs, and 8-12 rectal biopsies will be collected. A rectal swab will be collected for testing for gonorrhea and chlamydia to be performed by CDC. If positive for gonorrhea or chlamydia, men will be referred for care at their private physician's office, the health department, or AID Atlanta for treatment. All men will be instructed to place nothing in the rectum and to abstain from sex for 7 days after the procedure to allow the mucosa to heal.

# Phase II

40 participants (20 in each study arm) will be enrolled in study phase 2.

Study visit 2 will occur 1-6 weeks after the screening visit. During visit 2, the study group assignment will be reviewed and participants will be provided with a single dose of Truvada® or Genvoya®. Drug will be dispensed through the Emory Investigational Drug Service. Depending on the study arm they were assigned to, MSM will be dispensed 1 day of Truvada® or Genvoya® and instructed on dosing for that day. Four to six hours after the drug is taken, a urine sample, 4 tablespoons of blood will be drawn from the participants arm, as well as, penile and urethral swabs will be collected from participants. These sample will be used at CDC to develop an assay to detect Truvada® and Genvoya® in the body. All specimens will be coded with a unique numeric identifier such that the CDC laboratories that receive the specimens will be unable to link them back to the study participants. Participants will be requested to abstain from receptive anal intercourse 3 days prior to study visit 2 and while taking study product.

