For this protocol, we will recruit HIV-negative MSM and TGW who are not on hormone therapy aged 18-49 and who are willing to adhere to study procedures. There will be 3 phases, with 2 study visits for phase I, 3 study visits for phase II, and 4 study visits for phase III that will be conducted over a maximum period of 12 weeks. Participants are allowed to participate in more than one phase if a recovery or washout period occurs 8 weeks in between each phase. The first visit for all phases (phase I, phase II, and phase III) will be a screening visit where eligibility is determined, written informed consent is obtained, screening tests are performed, and men will be randomized to one of two study groups: 1. Use of oral Truvada®; or 2. Use of oral Genvoya®. During the second study visit (visit 2), men in phase I will not receive product, but will come in for blood work, urine sample, 2 pre-wet penile swabs, urethral swab, rectal swab, and rectal biopsy sampling. Participants who are in phase II will receive a single dose of the study product during visit 2, 1-6 weeks after the screening visit. MSM will return 4 to 6 hours after taking the drug for a urine sample. We will then collect 4 tablespoons of blood from the participants arm, in addition to, 2 pre-wet penile swabs, and a urethral swab. The third study visit will occur 24 hours from dosing time for MSM in phase II. Men will undergo a blood draw, urine sample, penile, urethral, and rectal swab, and rigid sigmoidoscopy for collection of rectal secretions and biopsies. Participants in phase III at study visit 2 will receive a 10-day supply of the study drug and will be instructed to take it for 10 consecutive days. For visit 3 in phase III, participants will return for a blood draw, urine collection, 2 pre-wet penile swabs, and a urethral swab to examine drug levels after 3-5 days of taking study drug. They will then return 10 days from dosage for visit 4, where blood, urine, penile, urethral, and rectal swabs will be collected, and rectal biopsy sampling will occur. All specimens will be transported directly to the laboratory of [name] at CDC where multiple immune assays are planned to determine the ability of these agents to penetrate mucosal tissues and potentially prevent HIV infection during RAI exposure.

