# **INCLUSION CRITERIA FOR MSM**

- 1) HIV-negative man who reports receptive anal sex with another man in the last 6 months
- 2) Male to female transgender women who have sex with men who report receptive anal intercourse with another man in the last 6 months and are not currently taking hormonal therapy or plan to take hormonal therapy for the duration of the study
- 3) Aged 18-49 years
- 4) Not currently taking PrEP and no plans to initiate during study
- 5) Able to provide informed consent in English
- 6) No plans for relocation in the next 3 months
- 7) Willing to undergo peripheral blood and rectal biopsy sampling
- 8) Willing to use study products as directed
- 9) Willing to abstain from receptive anal intercourse 3 days prior to starting study product and for the duration of the study and for 7 days after any rectal biopsy procedure.

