# EXCLUSION CRITERIA

- History of inflammatory bowel disease or other inflammatory, infiltrative, infectious or vascular condition involving the lower gastrointestinal tract that, in the judgment of the investigators, may be worsened by study procedures or may significantly distort the anatomy of the distal large bowel
- 2) Significant laboratory abnormalities at baseline visit, including but not limited to:
  - a) Hgb  $\leq$  10 g/dL
  - b) PTT > 1.5x ULN or INR > 1.5x ULN
  - c) Platelet count <100,000
  - d) Creatinine clearance <60

- Any known medical condition that, in the judgment of the investigators, increases the risk of local or systemic complications of endoscopic procedures or pelvic examination, including but not limited to:
  - a) Uncontrolled or severe cardiac arrhythmia
  - b) Recent major abdominal, cardiothoracic, or neurological surgery
  - c) History of uncontrolled bleeding diathesis
  - d) History of colonic, rectal, or vaginal perforation, fistula, or malignancy
  - e) History or evidence on clinical examination of ulcerative, suppurative, or proliferative lesions of the anorectal or vaginal mucosa, or untreated sexually transmitted disease with mucosal involvement
- 4) Continued need for, or use during the 14 days prior to enrollment, of the following medications:
  - a) Aspirin or more than 4 doses of NSAIDs
  - b) Warfarin, heparin (low-molecular weight or unfractionated), platelet aggregation inhibitors, or fibrinolytic agents
  - c) Any form of rectally administered agent besides products lubricants or douching used for sexual intercourse
- 5) Continued need for, or use during the 90 days prior to enrollment, of the following medications:
  - a) Systemic immunomodulatory agents
  - b) Supraphysiologic doses of steroids
  - c) Experimental medications, vaccines, or biologicals
- 6) Intent to use HIV antiretroviral pre-exposure prophylaxis (PrEP) during the study, outside of the study procedures
- 7) Symptoms of an untreated rectal sexually transmitted infection (e.g. rectal pain, discharge, bleeding, etc.)
- 8) Current use of hormonal therapy
- 9) Any other clinical condition or prior therapy that, in the opinion of the investigator, would make the patient unsuitable for the study or unable to comply with the study requirements.

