# Phase III

40 participants (20 in each study arm) will be enrolled in study phase 2.

Study visit 2 will occur 1-6 weeks after the screening visit. During visit 2, the study group assignment will be reviewed and participants will be provided with a 10 day supply of Truvada® or Genvoya®. Drug will be dispensed through the Emory Investigational Drug Service. Depending on the study arm they were assigned to, MSM will be dispensed 10 days of Truvada® or Genvoya® and instructed on dosing for 10 consecutive days prior to their scheduled study visit 4. MSM will be requested to abstain from receptive anal intercourse while on study product. Participants will be scheduled to return for their third study visit after taking the study product for 3-5 consecutive days.

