Acquisition of HIV drug resistance is a theoretic concern for those taking Truvada® or Genvoya® for PrEP. However, clinical trials of Truvada® for PrEP have shown this to be a very rare event except in those who were 'acutely' infected with HIV at the time of study enrollment. In the iPrex study, there was no drug resistant virus detected in 100 MSM who became infected after enrollment. Of the ten men who were identified retrospectively to be acutely infected with HIV at enrollment, drug resistance was detected in 2/2 of men in the active drug arm and 1/8 of men in the placebo arm^6. For this protocol, we will test men for HIV at study entry and monitor clinically for high-risk behavior or any signs of acute HIV infection at study visits. If high risk behavior (e.g. unprotected anal intercourse with a man of unknown HIV status) or symptoms of acute HIV infection are reported, and HIV antibody test will be repeated and the participant will be counseled about the need for any follow-up testing. Clinical signs and symptoms of acute HIV infection that will be queried include: fever, fatigue, malaise, skin rash, swollen glands, oral/genital ulcers, myalgia/arthralgia. [name] will review all reports of clinical signs/symptoms to determine appropriate follow-up and linkage to care as necessary. If a diagnosis of acute HIV infection is thought to be possible or determined by repeat HIV testing, the participant will be discontinued from the study.. For this protocol, we will test men for HIV at study entry and monitor clinically for high-risk behavior or any signs of acute HIV infection at study visits.

Men will be asked to abstain from receptive anal intercourse while using drug during the study protocol in order to limit additional exposures (e.g. semen, douching, additional

Version 6 04/21/17

lubricants) to the rectal mucosa. Men taking Truvada® or Genvoya® will be counseled that they should not expect to achieve protection from HIV infection by taking drug during this study, as they will be provided a limited supply. All men included in the study that have an interest in taking PrEP for HIV prevention, will be referred to an area PrEP provider at the termination of the study. The Hope Clinic has compiled a resource sheet of area providers that will be distributed to interested participants.

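### Abstinence before the rectal biopsy is specified inconsistently across phases, so comparing mucosal markers with the Phase I baseline, or between Phases II and III, may mix recent intercourse with drug exposure

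*Protocol*

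**What the plan says.** Two kinds of text bear on this point.

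**Eligibility.** Protocol, Inclusion Criteria, item 9, applies to every participant: "Willing to abstain from receptive anal intercourse 3 days prior to starting study product and for the duration of the study". It then adds 7 days after any biopsy.

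**Visit instructions and risk section.**
- Phase I, visit 2: the only restriction follows the biopsy: "All men will be instructed to place nothing in the rectum and to abstain from sex for 7 days after the procedure". The Lay Summary confirms that "men in phase I will not receive product".
- Phase II, visit 2: "Participants will be requested to abstain from receptive anal intercourse 3 days prior to study visit 2 and while taking study product". The biopsy comes at visit 3, 24 hours after the dose.
- Phase III, visit 2: "MSM will be requested to abstain from receptive anal intercourse while on study product", repeated at visit 3. The biopsy comes at visit 4, after 10 days of dosing. The 3-day lead-in is not mentioned.
- Risk of Genvoya®: the request applies while drug is being used, "in order to limit additional exposures (e.g. semen, douching, additional" lubricants, with the rectal mucosa named as the site to be protected.

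The Abstract says the Phase I biopsy is there to establish baseline values. Phases II and III each schedule one biopsy, after dosing. The Goal covers mucosal inflammatory effects as well as pharmacokinetics. The SAP describes tests of drug levels only.

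**The concern.** The protocol treats intercourse, and what comes with it, as an unwanted exposure of the tissue to be biopsied, but its visit text ties the control to dosing. Phase I men are not dosed, so on that text nothing reaches the one set of biopsies that can show the undosed state. Dosed men also get different lengths of control depending on their phase.

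The Phase I reference matters because a mucosal effect common to both drugs cannot be seen by comparing one drug with the other. If recent intercourse shifts cytokines or target cells, a dosed-versus-Phase I difference would contain that shift as well as any drug effect, and a Phase II versus III difference would mix length of dosing with length of abstinence. Every enrolled participant reports receptive anal intercourse in the previous 6 months, so recent exposure is plausible.

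The problem could not be repaired afterwards from the data described. The confidentiality section mentions behavioural data at study entry in general terms, and participants are monitored for high-risk behaviour at visits to decide on HIV testing. Nothing says that time since last intercourse, douching or rectal product use is recorded at the biopsy.

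**Working it through.** **1. The plan's own figures.** Enrolment: 2 × (5 + 20 + 20) = 90. Expected completers: 90 × (1 − 0.20) = 72. Both match the protocol. The inconsistency does not depend on them; they only give the group sizes used in step 5.

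**2. Abstinence requested before biopsy, from the visit text.**

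| Phase | Request before biopsy | Biopsy | Days |
|---|---|---|---|
| I | none | visit 2, no product | 0 |
| II | 3 days before visit 2, then on product | 24 hours after dose | 3 + 1 = 4 |
| III | on product | after 10 days of dosing | 10, or 3 + 10 = 13 with criterion 9's lead-in |

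**3. The same count from criterion 9 read literally.** Assume abstinence runs from screening, with visit 2 at 1 to 6 weeks:
- Phase I: 7 to 42 days.
- Phase II: add 1 day, giving 8 to 43.
- Phase III: add 10 days, giving 17 to 52.

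On this reading Phases I and II differ by about 1 day, and Phase III exceeds Phase II by 10 − 1 = 9 days for the same visit 2 timing. The two readings therefore give very different pictures of the Phase I baseline. The literal reading has its own difficulties. The 3-day lead-in adds nothing if abstinence is study-long, and it has no anchor in Phase I, where no product is started. Men entering a second phase skip visit 1 after a gap of at least 8 weeks, and the documents do not say whether that gap is covered.

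**4. Would one common minimum equalise the phases?** Let the minimum be k days before every biopsy. Phase III men also abstain through 10 dosing days, so their interval is the larger of k and 10. For any k below 10 they still abstain longer than the k days asked of the other phases. A common minimum would align Phase I with Phase II, but would not by itself align Phase II with Phase III.

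**5. Illustration on assumed values, none of them in the documents.** Let a fraction f of Phase I men have had recent intercourse that raises a marker by d standard deviations. Suppose no dosed men had, the drug has no effect, markers are normal and the groups are independent. The apparent drug effect (dosed minus Phase I) is −f × d. False-positive rates are from 4,000 simulated two-sided Wilcoxon rank-sum tests at the 5% level.

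| f | d | Apparent effect (SD) | 10 vs 40 men | 5 vs 20 men |
|---|---|---|---|---|
| 0 | – | 0 | 4–5% | 4% |
| 0.3 | 0.5 | −0.15 | 7% | 5% |
| 0.5 | 1.0 | −0.50 | 24% | 13% |
| 0.7 | 1.0 | −0.70 | 43% | 23% |

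If intercourse lowers the marker, the sign reverses. If Phase I men abstain as criterion 9 says, f is 0 and the problem disappears. The table shows only that the effect could range from negligible to large. It does not estimate the bias in this trial.

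**The case against.** The strongest reply is that criterion 9 already covers everyone. The Phase II and III instructions cannot narrow anything for Phase I, no passage says the request applies only during dosing, and silence in the Phase I visit text is not a waiver. This stands far enough that a flat statement that Phase I men are asked for no abstinence would be wrong. The Phase I visit instructions contain no such request, while the eligibility criterion asks for willingness. The conflict between the passages remains.

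The second reply is that the comparison in question is not a planned analysis. The Abstract names the comparison between arms, and the SAP has neither a test of inflammation nor a cross-phase test. This stands too. The comparison is implied by the purpose of the Phase I biopsy and by the Goal, not pre-specified.

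A reader might go further in three ways that the documents do not support:
- **That the Phase I reference is inflated, so an irritating drug will look harmless.** The protocol's stated reason is to limit exposures, not inflammation. The direction is an inference.
- **That all 10 Phase I men are affected.** A missing instruction is not behaviour. Only men with recent exposure could be affected, and their number is unknown.
- **That douching and lubricants are permitted on study.** Exclusion 4(c), "Any form of rectally administered agent besides products lubricants or douching used for sexual intercourse", screens need or use in the 14 days before enrolment. It grants no permission during abstinence, although the plan never says outright whether the abstinence request covers these products.

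**Conclusion.** The point holds as an inconsistency with a conditional consequence. Criterion 9 sets a study-long expectation, while the visit text gives 0, about 4, and 10 days (13 with the omitted lead-in) before biopsy in Phases I, II and III. If the visit text is what participants hear, comparisons of mucosal markers with Phase I, or between Phases II and III, may be confounded by recent rectal exposure, and nothing described in the plan would allow adjustment.

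This rests on two assumptions: that staff follow the visit instructions, and that recent intercourse affects the markers measured. The documents establish neither, and they give no size or direction. The inference that the trial's main comparison is biased is not supported, because both arms within a phase receive the same instruction. The point is a modest one, worth acting on because the remedy is cheap.

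**What to change.** - **Reconcile the text.** Bring inclusion criterion 9, the Phase I, II and III visit instructions and the abstinence paragraph under Risk of Genvoya® into one instruction, anchored to the biopsy and applied in every phase, including Phase I before visit 2. The investigators should choose the interval.
- **State its scope.** Say whether it covers douching and lubricants as well as intercourse.
- **Record the exposure.** At each biopsy visit, ask for days since last receptive intercourse, last douching and last rectal product use. Cross-phase comparisons can then be adjusted or restricted, which is still needed because a common minimum alone will not equalise Phases II and III.

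The cost is revised wording, a few questions per biopsy visit, and slightly more burden for the 10 Phase I men, who already had to declare willingness under criterion 9. If the Phase II interval is lengthened, the 40 Phase II men carry some of that burden as well.
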